5.1 Registration with the Masonic Cancer Center Clinical Trials Office

Any patient who has been consented is to be registered in OnCore by the Study Coordinator or designee. If a patient is consented, but not enrolled, the patient's record is updated in OnCore as a screen failure and reason for exclusion recorded.

5.2 Study Enrollment with the Masonic Cancer Center Clinical Trials Office

To be eligible for study enrollment, the patient must sign the treatment consent and meet each of the inclusion criteria and none of the exclusion on the eligibility checklist based on the eligibility assessment documented in the patient's medical record.

The Study Coordinator or designee will assign the study treatment arm to complete enrollment.

5.3 Patients Who Are Enrolled and Do Not Receive Study Treatment

If a patient is enrolled in the study and is later found not able to begin exemestane, for whatever reason, the patient will be removed from study and treated at the physician's discretion. The PCRC or designee will update OnCore of the patient's non-treatment status. The reason for removal from study prior to starting study treatment will be clearly indicated in OnCore. The patient will be replaced to complete enrollment.

6 Treatment Plan

In order to provide optimal patient care and to account for individual medical conditions, investigator discretion may be used in the prescribing of all supportive care drug therapy. Refer to Section 6.3 for prohibited medications during exemestane therapy.

6.1 Exemestane Dosing Plan

Exemestane is self-administered as a single, 25 mg tablet by mouth following a meal once daily at approximately the same time each day. If the dose is missed by more than 8 hours, the patient will skip that dose and take the next scheduled dose at the usual time.

Exemestane will continue once daily until disease progression, unacceptable side effects, patient refusal/non-compliance, or the treating physician feels discontinuing therapy is in the best interest of the patient.

The patient will be provided with a daily drug log to record the time of administration, side effects, and any missed doses. The patient will be instructed to bring the drug log and study drug bottles (including any empties) to each appointment for reconciliation.

During the first treatment cycle only, the patient will be contacted by a member of the research staff 8 to 12 days after dosing was started to inquire "how things are going" and to see if she has any questions or concerns.

For the purpose of this study each 3 week (21 day) dosing period will be considered a treatment course. A disease re-assessment will be done after every 2 treatment courses.

Participants who do not undergo the 1st disease re-evaluation will be considered unevaluable and replaced.

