This is a phase II study of daily oral exemestane for the treatment of advanced non-small cell lung cancer in post-menopausal women who are progressing on an FDA approved immune checkpoint blockade therapy. The study will be conducted using Simon's two-stage design.³⁰ Stage 1 will enroll 10 patients. If at least 2 objective responses are observed at the first disease re-evaluation at 6 weeks after beginning oral exemestane, Stage 2 will be activated. In Stage 2, an additional 19 patients will be enrolled for a total of 29 patients. If 4 or more objective responses are observed in the 29 patients, exemestane will be deemed worthy of further investigation in this patient population.

4 Patient Selection

Study entry is open to post-menopausal women regardless of race or ethnic background. While there will be every effort to seek out and include minority women, the patient population is expected to be similar to that of advanced non-small cell cancer lung studies at the University Of Minnesota. Men are not eligible for this study as exemestane works by suppressing estrogen production. Women of child-bearing potential are not eligible as exemestane is FDA pregnancy category X – known harm to the unborn.

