6.4 Duration of Study Treatment

Treatment continues for a minimum of 2 cycles (6 weeks) and then until disease progression unless one of the following occurs:

- Patient experiences unacceptable side effects exemestane
- Patient refuses further treatment or is non-compliant
- Patient requires other anti-cancer therapy
- A greater than 6 week break from exemestane therapy occurs, regardless of cause
- In the opinion of the treating investigator, continuing on study therapy is not in the best interest of the patient

Exemestane may be continued as a single agent at the discretion treating investigator in the event the ICB therapy is permanently discontinued due to

unacceptable toxicity (refer to Appendix IV for potential risks of ICB therapy) as long as none of the above criteria is not met.

An end of treatment visit occurs 4 weeks (\pm 1 week) after the last dose of exemestane or prior to the start of a new therapy, whichever is shorter, to assess for ongoing toxicity and for the patient to return their study drug supply and daily drug log.

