Drug Accountability: The study drug supply will be stored and dispensed by the University of Minnesota Medical Center, Fairview Investigational Drug Services (IDS) Pharmacy. IDS will be responsible for drug accountability through the study. IDS will provide study drug to participating MNCCTN sites.

Dosage and Administration Schedule: One 25 mg tablet once daily after a meal

Dose Forms and Strengths: Aromasin Tablets are round, biconvex, and off-white to slightly gray. Each tablet contains 25 mg of exemestane. The tablets are printed on one side with the number "7663" in black.

Storage and Stability: Store at 25°C (77°F); excursions permitted to 15°–30°C (59°–86°F).

Drug Return/Destruction: At the end of the study and after final reconciliation, IDS will destroy any remaining drug according to their current SOP.

Expected Side Effects: refer to Section 6.1.1.

FDA Pregnancy Category X

Contraindications and Counseling:

Patients with a known hypersensitivity to the drug or to any of the excipients

Women of premenopausal endocrine status, including pregnant women

Patients should be informed that they should not take estrogen-containing agents while they are taking exemestane as these could interfere with its pharmacologic action.

Patients should be informed that AROMASIN lowers the level of estrogen in the body. This may lead to reduction in bone mineral density (BMD) over time. The lower the BMD, the greater the risk of osteoporosis and fracture.

Refer to the Aromasin Prescribing Information ([https://www\(pfizer.com/products/product-detail/aromasin](https://www(pfizer.com/products/product-detail/aromasin)) for additional information

8 Measurement of Effect

For the purposes of this study's primary endpoint, patients should be re-evaluated for response every 6 weeks.

Response and progression will be evaluated in this study using the revised Response Evaluation Criteria in Solid Tumors (RECIST) guideline (version 1.1) [*Eur J Ca* 45:228-247, 2009]. Refer to Appendix II for the complete RECIST guidelines.

Quality of life scores, as measured by PROMIS, will be evaluated descriptively at baseline, every 3 weeks during and at the end of treatment visit using medians, ranges, interquartile ranges and boxplots to look for trends in various areas measured by PROMIS.

9 Schedule of Activities

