Note: Study visits are scheduled every 3 weeks independent of the immune checkpoint blockade therapy administration per standard of care. During exemestane a ± 2 day window is permitted for every 3 week visits (start of new treatment cycle) and a ± 7 day window is permitted for the every 6 week disease reassessment. The end of treatment (EOT) visit 30 days after the last dose of study drug may be performed with a ± 7 day window. Follow-up visits are per standard of care with disease status and survival status abstracted from the medical record.

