9.1 Schedule of Patient Tests and Procedures

	Baseline (within 14 days of enrollment)	During Exemestane Therapy		End of Treatment Visit 4 weeks \pm 1 week) after final dose of exemestane	Follow-up	
		Every 3 weeks (\pm 2 days)	Every 6 weeks (\pm 1 week)		disease response (until PD or start of new therapy)	survival at 1 year (all patients)
ASSESSMENTS						
Witten consent	X					
Medical history	X	X		X		
Review of prior anti-cancer therapy	X					
Concomitant meds	X	X				
Physical exam	X	X				
Vital Signs	X	X				
Weight	X	X				
ECOG Performance status	X	X				
Disease re-assessment			X		X	
Symptom and toxicity notation (pt diary)	X	X		X		
LABORATORY EVALUATIONS						
CBC/diff, plts	X	X				
Comprehensive Metabolic Profile (CMP)	X	X				
Estradiol assay ²	X					
SCANS AND PROCEDURES						
CT of chest/abd/pelvis	X ¹		X	X (if not done in previous 6 weeks)	X ⁴	
MRI or CT of brain if previous hx of CNS dz or as clinically indicated	X ¹					
DEXA scan	X ¹ (perform only if none in previous 12 months)	repeat every 12 months				
CONTINUATION OF STANDARD OF CARE IMMUNE CHECKPOINT INHIBITOR THERAPY						
Nivolumab pembrolizumab, or atezolizumab	Continue per SOC while maintaining every 3 week visits for exemestane					
RESEARCH RELATED						
Exemestane		25 mg po once a day every day				
Research staff "check-in" ³		Cycle 1 only between Day 8 and 12				
Reconciling of Exemestane tablets		X		X		
Quality of Life Questionnaire (PROMIS-29 Profile)	X	X		X		
Monitoring for stopping rule events		Refer to Section 10.3				
Blood Samples 30 ml serum (red top) 20 ml EDTA (purple top) 20 ml cell-free DNA BCT tube	X	X prior to cycle 2, 3, and 5		X		
Blood Samples 10 mL green top tube for PBMC	X	X prior to Cycle 2 and 3				
biopsy material ⁵	X	at the time of biopsy for clinical reasons				

1 Within 4 weeks of study enrollment

2 For women < 55 years of age

- 3 A member of the research staff will contact the patient to see how things are going (screen for toxicity) and if they have any questions
- 4 Per standard of care for patients who discontinued exemestane for reasons other than disease progression – abstract results from medical record
- 5 At enrollment archived from original diagnosis will request 15 unstained slides but require a minimum of 5 unstained slides for eligibility or resection and fresh at any time tissue is obtained for clinical reasons (i.e. SOC) - consent for tissue is embedded in the treatment consent

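### Section 6.1 replaces treated women who die, decline or change therapy before the first scan, so early treatment failures can drop out of the response denominator and both stage counts

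*Combined protocol and SAP*

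**What the plan says.** Two replacement rules apply.

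- Section 5.3 covers women who enrol but never start exemestane: "The patient will be replaced to complete enrollment".
- The last sentence of Section 6.1 goes further: "Participants who do not undergo the 1st disease re-evaluation will be considered unevaluable and replaced". Because 5.3 already deals with the untreated, this sentence adds treated women, and it gives no exception by reason.

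Section 3 places the Stage 1 count "at the first disease re-evaluation at 6 weeks after beginning oral exemestane". Section 13.1 counts responses among 10 and then 29 patients. Section 13.3 reports a simple proportion with a 95% confidence interval. Neither defines the analysis population or says how a missing first assessment is handled.

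Section 8 sets the response standard: "Response and progression will be evaluated in this study using the revised Response Evaluation Criteria in Solid Tumors (RECIST) guideline", and refers to Appendix II. To be evaluable there, a woman needs measurable baseline disease, at least one cycle and a re-evaluation. One exception is added: objective progression before the end of cycle 1 is evaluable. Death and unimaged decline have no such exception. Appendix II labels the latter symptomatic deterioration and asks for efforts to document progression later, but does not assign these women to non-response.

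**The concern.** All women enter with disease progressing on checkpoint blockade, and ECOG performance status 2 is allowed. Death, clinical decline or a switch of therapy before week 6 is therefore foreseeable, and each is a failure of the study treatment. A responder is much less likely to miss the scan for such a reason.

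Replacing these women removes failures from the denominator and gives a new woman the chance to respond. In Stage 1 there are only 10 places, so one or two replacements mean one or two extra chances of reaching the 2 responses needed to continue. The same happens in the final count of 4 among 29 and in the reported proportion.

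**Working it through.** **Who is lost under the text as written**

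- *Death or unimaged decline before the scan.* She has had no re-evaluation, so 6.1 replaces her, and Appendix II does not make her evaluable.
- *Early new therapy.* Section 9.1 asks for an end-of-treatment CT only "if not done in previous 6 weeks". The baseline CT, allowed "Within 4 weeks of study enrollment", can satisfy this, because 6.4 times the visit 4 weeks (give or take 1 week) "after the last dose of exemestane or prior to the start of a new therapy, whichever is shorter". Example: baseline CT 1 week before the first dose, drug stopped at week 2, new therapy at week 4. The last CT is then 1 + 4 = 5 weeks old, so no scan is required and she is replaced.
- *Early stop without new therapy.* The visit falls 4 weeks after the last dose. The baseline CT suffices only if the drug stops within 6 − 4 = 2 weeks of that CT (6 − 3 = 3 weeks at the edge of the visit window). This route is narrow.
- *Imaged progression before the scheduled scan.* She is not lost. Before the end of cycle 1 the Appendix II exception applies. After that she has had a cycle and a re-evaluation.

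**The plan's own design figure**

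Inputs from 13.1 and 13.2: null rate 5%, alternative 20%, n1 = 10, N = 29, continue with at least 2 responses, success with at least 4.

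P(success) = Σ over x ≥ 2 of Bin(x; 10, p) × P(Bin(19, p) ≥ 4 − x)

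At p = 0.05 the terms are 0.0183 (x = 2), 0.0065 (x = 3) and 0.0010 (x ≥ 4), which sum to 2.6%. At p = 0.20 the result is 59.6%. An exhaustive search for Simon's optimal design returns the same 10, 29 and 4, but with a Stage 1 threshold of at least 1 response (error 4.7%, power 80.1%). That mismatch is a separate issue; it is used below only to show sensitivity.

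**Effect of replacement**

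Assumptions, not in the documents: a share d of treated women is replaced, all are non-responders, and the true rate in all treated women is 5%. The rate among counted women is then 0.05 / (1 − d). For d = 10% this is 0.05 / 0.90 = 0.0556, and the terms become 0.0251 + 0.0091 + 0.0015 = 3.6%.

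| Share replaced | Rate among counted | Stage 2 opens | False positive, written rule |
|---|---|---|---|
| 0% | 5.0% | 8.6% | 2.6% |
| 5% | 5.3% | 9.4% | 3.0% |
| 10% | 5.6% | 10.3% | 3.6% |
| 20% | 6.3% | 12.6% | 5.1% |
| 30% | 7.1% | 15.7% | 7.4% |

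The written rule reaches 5% at d = 19.6%. By count, with d = k / (29 + k): 1 replaced gives 2.9%, 3 give 3.5%, 7 give 5.0%.

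If half of a 10% share is missing for reasons unrelated to response, only the other half distorts the rate: 0.05 / 0.95 = 0.0526, and the false-positive rate is 3.0%.

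**Effect on the estimate** (exact 95% intervals)

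- Minimum success as reported: 4/29 = 13.8% (3.9 to 31.7).
- With 3 replaced women counted: 4/32 = 12.5% (3.5 to 29.0).
- With 7 replaced women counted: 4/36 = 11.1% (3.1 to 26.1).

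**The case against.** **The effect is small.** One to three replacements move the false-positive rate to between 2.9% and 3.5%, and the intervals above overlap almost fully. Shares of 20% to 30% have no support in the documents. This stands, and it limits the priority of the point. The margin does come from the strict Stage 1 threshold: with at least 1 response, which matches the stated 80% power, the rate is 5.5% at 5% replaced and 6.4% at 10%.

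**Safeguards exist.** Life expectancy must be 3 months or more (4.1.7). Women who stop without progression are followed for response until progression or new treatment (6.5), and the end-of-treatment CT catches others. These narrow the group, but the life-expectancy criterion is an opinion, and no text returns an early death, an unimaged decline or an early switch to the denominator.

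**Not every missing scan is a failure.** Section 6.4 also lists refusal, non-compliance, side effects and long breaks. This stands: treating all replaced women as non-responders is the upper end.

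**The null may refer to evaluable women.** Section 13.2 names no population. If 5% is the rate among evaluable women, replacement does not inflate the error. But 13.2 justifies the 5% by all women progressing on anti-PD1 therapy at entry, which describes everyone treated. On either reading the reported proportion leaves out early failures.

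**Imaged early progression.** A reader might infer that these women are lost too, since Section 3 puts the first re-evaluation at 6 weeks and Section 9 adds that a "7 day window is permitted for the every 6 week disease reassessment". The documents do not support this: 6.1 speaks of the first re-evaluation, not a week-6 scan, and Appendix II keeps such women evaluable. A cross-reference is enough.

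**Conclusion.** The concern holds for treated women who have no scan because they died, declined without imaging or started new therapy. Under the plan as written they are replaced, and the response proportion and both stage counts are biased upward.

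The direction is clear, but the size is not known and is probably modest. The calculated shifts rest on an assumed replacement share, on all replaced women being non-responders, and on the 5% null applying to all treated women.

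A reader might infer that the rule pushes the false-positive rate past the stated 5%. Under the written thresholds it does not, unless about one treated woman in five is replaced, and nothing in the documents suggests that many. Nor does the bias require every missing scan to count as non-response. That broader rule would lower power from 59.6% to 56.0% if 5% of would-be responders missed the scan for unrelated reasons (rate 0.20 × 0.95 = 0.19), and to 52.1% if 10% did (rate 0.18).

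The change is worth making because it costs little and settles the denominator before any data are read.

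**What to change.** Replace the last sentence of 6.1 with text to this effect:

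> A patient who has taken at least one dose of exemestane and who dies, progresses (objectively or clinically) or starts new anti-cancer therapy before the first re-evaluation is evaluable, counts as a non-responder toward the 10 and the 29, and is not replaced. Only patients who never start exemestane (5.3), or whose scan is missing for a documented reason unrelated to disease or treatment, are replaced.

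Then:

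- Name this denominator in 13.1 for both stage decisions and in 13.3 for the proportion and its interval.
- State that it governs over the evaluability paragraph in Appendix II, and cross-refer to that appendix for imaged early progression.
- Add a sensitivity analysis in all treated women, with any missing first scan counted as non-response.

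The cost is a few sentences and a recorded reason for each missing scan, with no new visits, scans or change of treatment. The reported response rate may be slightly lower. Deciding that a missing scan is unrelated to disease or treatment takes judgement; the sensitivity analysis shows whether that judgement matters.

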6.1.1 Exemestane Expected Toxicity

Based on extensive use in post-menopausal women with breast cancer as sourced through IBM Micromedex® available through the University of Minnesota Libraries:

In general, exemestane is well tolerated at this dose when given long term to post-menopausal women with breast cancer. It is thought that adding exemestane to ongoing immune checkpoint blockade the risks profile for neither drug will be different.

Rare, but potentially serious side effects

Bone loss. Exemestane lowers the level of estrogen in the body and may reduce bone mineral density (BMD) over time, possibly increasing the risk of bone fracture. A DEXA scan will be done at baseline, if none performed in the previous 12 months and every 12 months while receiving exemestane.

Chest pain, heart failure, or stroke. A small number of women had chest pain, heart failure, or a stroke while taking exemestane

Occurring in less than 1 out of 100 women

Gastric ulcer

Cholestatic hepatitis, hepatitis

Common side effects (occurring in 10 or more out of 100 women)

- hot flashes
- fatigue
- joint pain
- headache
- insomnia
- increased sweating
- depression
- feeling anxious
- upset stomach
- difficulty breathing
- hair loss or thinning
- an increase by a blood test of a liver enzyme (alkaline phosphatase) that may indicate a bone disorder or liver disease

Use of estrogens (such as hormone replacement therapy or HRT) and phytoestrogen supplements (such as black cohosh) to relieve the menopausal like side effects are prohibited during exemestane treatment.

Only post-menopausal women are enrolled in this study as taking exemestane during pregnancy is known to cause birth defects and/or miscarriages.

Refer to the prescribing information for additional details.

We do not expect any difference in the toxicity profile of exemestane when it is added to an ongoing treatment with anti-PD1 or anti-PDL1 antibody treatment. There are ongoing clinical trials in breast cancer using the combination of hormone therapy and an immune checkpoint blockade.

6.1.2 Exemestane Dose Interruptions and Modifications

There are no dose reductions/modifications recommended for exemestane related toxicities; however patients should be treated according to Institutional practices. If a patient experiences a Grade 4 toxicity felt at least possibly related to exemestane, the study drug will be discontinued per Section 6.4. Patients will not make up missed or vomited doses of exemestane.

6.2 Immune Checkpoint Blockade Therapy

All patients will continue treatment with their prior anti-PD1 or anti-PDL1 antibody treatment as per standard of care.

Dose delays or modifications for the ICB agent will be per standard of care and independent of exemestane therapy. A summary of the expected toxicity for each of the three possible ICB agents is provided in Appendix IV.

ICB therapy will be obtained through the same mechanism and will continue to be charged to the patient and her third party payer as before study enrollment.

If the ICB therapy is delayed, exemestane therapy should continue as medically appropriate.

Exemestane may be continued at the discretion of the treating investigator if the ICB therapy is permanently discontinued.

6.3 Supportive Care and Prohibited Medications

Commercially available palliative and supportive care for disease-related symptoms should be offered to all treated patients.

Patients with pre-existing osteoporosis should be on treatment with calcium/vitamin D and/or bisphosphonates.

Patients must be instructed not to take any additional medications (including over-the-counter products) during the study without prior consultation with her study doctor. Use of estrogens (i.e. hormone replacement therapy) and phytoestrogen supplements (i.e. black cohosh) are prohibited during exemestane treatment.

Concomitant use of strong CYP 3A4 inducers decreases exemestane exposure therefore their use will be prohibited. For a list of CYP34A inducers refer to Appendix III.

No chemotherapy, hormonal anticancer therapy, or experimental anticancer medications other than those study related will be permitted while the patient is on study. Any disease progression requiring other forms of specific anti-tumor therapy will be cause for discontinuation from the study.

